4.3.2. Subject Exclusion Criteria

Subjects eligible to participate in this study must not meet any of the following exclusion criteria:

1. Has plans to become pregnant during the course of the study or is currently pregnant or breastfeeding.
2. Plans to receive a licensed flavivirus vaccine or participate in another flavivirus vaccine trial during the study.
3. Has positive serology for HIV 1/2, Hepatitis C virus, or Hepatitis B surface antigen.
4. Has known or suspected congenital or acquired immunodeficiency, or recent history or current use of immunosuppressive therapy*

**Anti-cancer chemotherapy or radiation therapy within the preceding 6 months, or long-term (at least 2 weeks within the previous 3 months) systemic corticosteroids therapy (at a dose of at least 0.5 mg/kg/day). Intranasal or topical prednisone (or equivalent) is allowed.*

5. Had organ and/or stem cell transplantation whether or not on chronic immunosuppressive therapy.
6. Has history of malignancy other than squamous cell or basal cell skin cancer, unless there has been surgical excision that is considered to have achieved cure*.

**Subjects with a history of skin cancer must not be vaccinated at the previous tumor site.*

7. Has history of chronic or acute severe neurologic condition*.

**Including history of Guillain-Barre syndrome, seizure disorder or epilepsy, Bell's palsy, meningitis, or disease with any focal neurologic deficits.*

8. Has diabetes mellitus type 1 or type 2, including cases controlled with diet alone.

**Note: history of isolated gestational diabetes is not an exclusion criterion.*

9. Has history of thyroidectomy, or thyroid disease requiring medication during the last 12 months.

10. Has major psychiatric illness during last 12 months that in the investigator's opinion would preclude participation.

11. Has history of other chronic disease or condition*.

**Includes the conditions and diagnoses defined as AESI in Section 9, as well as autoimmune disease, hypercholesterolemia, chronic hepatitis or cirrhosis, chronic pulmonary disease, chronic renal disease, and chronic cardiac disease including hypertension even if medically controlled*

– Vital signs must be normal by protocol toxicity grading scale or determined to be normal-variant by investigator. In the event of an abnormal heart rate or blood pressure due to physiological variation or activity, the subject may rest for 10 minutes in a quiet room, and then blood pressure and/or heart rate may be re-measured. Repeated vital signs may be used to determine eligibility.

12. Has current or past history of substance abuse that in the investigator's opinion would preclude participation.

13. Has tattoos, scars, or other marks on both deltoid areas that would, in the opinion of the investigator, interfere with assessment of the vaccination site.

14. Has a history of chronic urticaria (recurrent hives).

15. Has known allergy or history of anaphylaxis or other serious reaction to a vaccine or vaccine component*.

**Including aluminum hydroxide (alum) or aminoglycosides (e.g., neomycin and streptomycin).*

16. Had major surgery (per the investigator's judgment) in the month prior to screening or plans to have major surgery during the study.

17. Received blood products or immunoglobulin in the 3 months prior to screening or planned use during the course of the study.

18. Donated a unit of blood within 8 weeks before Day 1 or plans to donate blood during the course of the study.

19. Received live attenuated vaccine from 30 days before Day 1 or plans to receive a live attenuated vaccine from Day 1 until 30 days after the last vaccination.

20. Received killed or inactivated vaccine from 14 days before Day 1 or plans to receive a killed or inactivated vaccine from Day 1 until 14 days after the last vaccination.

21. Received experimental therapeutic agents within 3 months prior to the first study vaccination or plans to receive any experimental therapeutic agents during the course of the study.

22. Is currently participating or plans to participate in another clinical study involving an investigational product, blood drawing, or an invasive procedure listed below.

**An invasive procedure requiring administration of anesthetics or intravenous dyes or removal of tissue would be excluded. This includes endoscopy, bronchoscopy, or administration of IV contrast.*

23. Has an acute illness or temperature $\geq 38.0^{\circ}\text{C}$ on Day 1 or Day 29* or within 2 days prior to vaccination.

**Subjects with fever or an acute illness on the day of vaccination or in the 2 days prior to vaccination may be re-assessed and enrolled if healthy or only minor residual symptoms remain within 2 days of Day 1 or Day 29.*

24. Is a study site employee* or staff paid entirely or partially by the OCRR contract or subcontract for the trial, or staff who are supervised by the PI or Sub-Investigators.

**Including the Principal Investigator, sub-Investigators listed in Form FDA 1572 or Investigator of Record Form*

25. In the investigator's opinion, the subject cannot communicate reliably, is unlikely to adhere to the study requirements, or has a condition that would limit their ability to complete the study.

4.4. Treatments

4.4.1. Treatments Administered

All subjects were to receive two doses of either 5 mcg ZPIV, 2.5 mcg ZPIV, or placebo administered intramuscularly 28 days apart.

4.4.2. Identity of Investigational Product(s)

ZPIV (Puerto Rico PRVABC59 strain), a formalin-inactivated whole virus vaccine produced by WRAIR, was administered in two intramuscular (IM) injections 28 days apart. Aluminum Hydroxide Adjuvant Alhydrogel® (aluminum hydroxide [or alum]) was used to adjuvant the ZPIV vaccine and to further dilute the adjuvanted vaccine for the 2.5 mcg dose. Use of alum as an adjuvant is well established and generally well tolerated.

4.4.3. Method of Assigning Subjects to Treatment Groups (Randomization)

Enrollment/randomization was performed through the enrollment module of AdvantageEDC, the electronic data capture system maintained by the SDCC. The list of randomized treatment assignments was prepared by statisticians at the SDCC and included in the enrollment module for this trial. The electronic data capture system assigned each subject a treatment code after the demographic and eligibility data have been entered into the system. A designated individual at each site was provided with a treatment key, which links the treatment code to the actual treatment assignment, to be kept in a secure place.

At the time of consent and upon entry of demographic data and confirmation of eligibility for this trial, the subject is enrolled. In group 1 (5 mcg ZPIV, N=45; placebo, N=5), two sentinel subjects were enrolled first and received ZPIV in an open-label fashion. All other subjects were randomized in a double-blind fashion. Upon completion of enrollment in Group 1, Group 2 subjects (2.5 mcg ZPIV, N=35; placebo, N=5) were randomized. Subjects received the same study product at their first and second investigational vaccinations.

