
Enrollment of the 2.5 mcg ZPIV group (Group 2) can begin after or at the same time non-sentinel subjects in Group 1 receive the 1st dose of vaccine. As of December 18, 2017, the majority of non-sentinel subjects in Group 1 have already received the 1st dose and have been followed until Day 8 for safety and reactogenicity, and no halting rules have been met or safety concerns identified. As this is a dose de-escalation study, concurrent enrollment of some remaining non-sentinel subjects in Groups 1 is permitted after enrollment of Group 2 subjects has begun; also, no sentinel subjects will be used in Group 2. All subjects in Group 2 will receive study product or placebo in double-blind fashion.

The original study design planned to enroll 40 ZPIV recipients and 5 placebo recipients in each Group. However, due a natural disaster (hurricane Maria), 11 subjects enrolled in Group 1 had loss of samples at key timepoints. To rebalance the number of evaluable subjects between Groups, Group 1 enrollment will be increased by 5 subjects and Group 2 enrollment will be decreased by 5 subjects, for a total enrollment of 50 subjects in Group 1 and 40 in Group 2. Treatment assignments for both groups will be assigned according to the originally planned 8:1 ratio of ZPIV:placebo. Without compromising the blind of the study, we can anticipate approximately 35 evaluable ZPIV recipients and approximately 5 evaluable placebo recipients in each group.

All subjects will receive a homologous boost of ZPIV or placebo 28 days post-prime if no halting rules precluding second vaccination are met ([Section 9](#)). All subjects will be monitored for occurrence of unsolicited AEs until 28 days after the second vaccination.

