## **5.4 Treatment Assignment Procedures**

### **5.4.1 Randomization Procedures**

Per International Conference on Harmonization (ICH) guideline E6: Good Clinical Practice (GCP), screening records will be kept at the VTEU subcontract site to document the reason why an individual was screened, but failed trial entry criteria. The reasons why individuals failed screening will be recorded in the Statistical and Data Coordinating Center's (SDCC) AdvantageEDCSM (Electronic Data Capture System).

Once consented and upon entry of demographic data and confirmation of eligibility for this trial, the subject will be enrolled. Two sentinel subjects in Group 1 will receive 5 mcg ZPIV open-

label. All other subjects will be dosed in double-blind randomized fashion. Subjects will receive the same study product and dose at their first and second study vaccinations. Subjects and investigators will be blinded as to study product received except for the sentinel subjects who will be dosed open label. Subjects and investigators will not be blinded to study group (1 or 2).

Enrollment of subjects will be done online using the enrollment module of AdvantageEDC. The list of randomized treatment assignments will be prepared by statisticians at the SDCC and included in the enrollment module for this trial. AdvantageEDC will assign each subject a treatment code after the demographic and eligibility data have been entered into the system. A designated individual at each site will be provided with a treatment key, which links the treatment code to the actual treatment assignment, which will be kept in a secure place.

Instructions for use of the enrollment module are included in the AdvantageEDC User's Guide. Manual back-up randomization procedures are provided in the MOP for use in the event that the site temporarily loses access to the Internet or the online enrollment system is unavailable.

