### 11.2 Sample Size Considerations

The sample size for this study was selected to obtain preliminary estimates of vaccine safety and immunogenicity in a time sensitive manner. This study is not designed to test a specific null hypothesis. As this is a phase I study of ZPIV, it is primarily designed to collect initial information about safety and immune responses of two different doses of the vaccine. Due a natural disaster (hurricane Maria), 11 subjects had loss of serum samples at key timepoints and will not be included in any immunogenicity analyses, resulting in approximately 35 evaluable active subjects and 5 placebo subjects in each dose group for those analyses. These 11 subjects will be included in the safety analysis population resulting in approximately 45 active subjects in the 5.0 mcg dose group and 35 active subjects in the 2.5 mcg dose group, for a total of approximately 80 subjects receiving at least one study vaccination of ZPIV.

The sample size in each dose cohort is small, thus the precision of estimate for AEs is limited. Rare AEs associated with dose are not demonstrable in a clinical study of this size; however the probabilities of observing one or more AEs within a dose group at the minimum dose sample size of 35 and also among the approximately 80 subjects receiving ZPIV are presented in the table below. The minimum detectable event rates to achieve various levels of power are also displayed.

If there are AEs associated with a particular dose of ZPIV, this study will have at least 80% power to observe at least one such event in a dose cohort if the true rate is 4.5%. If there are AEs associated with ZPIV overall, independent of dose, this study will have approximately 80% power to observe at least one such event in all ZIKV vaccine subjects if the true rate is 2.0%.

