6. GENERAL STATISTICAL CONSIDERATIONS

6.1. General Principles

All continuous variables will be summarized using the following descriptive statistics: n (non-missing sample size), mean, standard deviation, median, minimum and maximum, unless otherwise specified. The frequency and percentage of observed levels will be reported for all categorical measures; denominators for percentages will be defined for each analysis.

Listings will be provided for all data. Sort order will be specified on each listing shell in Appendix 3.

Summary tables will be structured with a column for each treatment group (2.5 mcg ZPIV, 5 mcg ZPIV, Placebo) and for all subjects for safety summaries.

All tables will be annotated with the total population size relevant to that table/group, including any missing observations.

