9.3.1. Solicited Events and Symptoms

Statistical comparisons of the frequency and duration of vaccine related Grade 3 local, systemic, or laboratory AE, and Grade 2 or greater local or systemic reactogenicity are presented post dose 1, post dose 2, and post any dose in [Table 43](#), overall and by pre-vaccination flavivirus immune status. Frequencies of each adverse event are compared between dosage groups using Fisher’s Exact test. The distribution of the duration of adverse events (excluding laboratory AEs) will be compared between all dosage groups using the 2-samples Wilcoxon rank sum test.

The frequency and proportion of subjects experiencing any local or systemic solicited event over the 8-day post-vaccination reporting period will be summarized by dose number, pre-vaccination flavivirus immune status, severity and treatment group in [Table 44](#) (post dose 1, post dose 2, and post any dose).

The number, percentage, and exact 95% CI of subjects experiencing each solicited event over the 8-day post-vaccination reporting period, collected in-clinic pre-vaccination, post-vaccination and via memory aid, will be summarized by pre-vaccination flavivirus immune status, dose number and symptom in [Table 45](#) (all subjects), [Table 46](#) (baseline ZIKV seropositive subjects), [Table 47](#) (baseline ZIKV seronegative subjects), [Table 48](#) (baseline ZIKV seropositive and DENV seropositive subjects), [Table 49](#) (baseline ZIKV seropositive and DENV seronegative subjects), [Table 50](#) (baseline ZIKV seronegative and DENV seropositive subjects), and [Table 51](#) (baseline ZIKV seronegative and DENV seronegative subjects).

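### The 5 mcg versus 2.5 mcg comparison is not randomised and is open by group, yet the SAP plans only unadjusted p-values for it, with no between-dose difference, interval or serostatus-adjusted estimate

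*SAP*

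**What the plan says.** **Allocation.** Protocol section 4 sets the randomisation within group: "Treatment assignments for both groups will be assigned according to the originally planned 8:1 ratio of ZPIV:placebo". Neither document gives a ratio or procedure for assigning a subject to 5 mcg or 2.5 mcg. SAP 4.4.3 describes sequential enrolment: "Upon completion of enrollment in Group 1, Group 2 subjects (2.5 mcg ZPIV, N=35; placebo, N=5) were randomized". Protocol section 4 is looser: "concurrent enrollment of some remaining non-sentinel subjects in Groups 1 is permitted after enrollment of Group 2 subjects has begun". SAP 4.1 also lets Group 2 start alongside the first doses of Group 1 non-sentinels.

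**Blinding.** Protocol 5.4.1: "Subjects and investigators will not be blinded to study group (1 or 2"). The blind covers ZPIV against placebo inside a group, not the dose level.

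**Analysis.** Primary objective 2 and primary endpoints 5 and 6 are comparisons between dosage groups. SAP 9.3.1 says "Frequencies of each adverse event are compared between dosage groups" by Fisher's exact test; duration is compared by a two-sample Wilcoxon test. The Table 43 shell prints counts, median durations and p-values, first for all subjects and then for six overlapping serostatus subgroups. It has no column for a between-dose difference, a ratio or an interval. The Fisher test in Table 12 (withdrawals and discontinuations) is across all three treatment groups.

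**Framing.** Protocol 11.2 states "This study is not designed to test a specific null hypothesis", and Protocol 11.1 calls the study exploratory. Protocol 11.1 also says comparisons will be stratified by pre-vaccination immune status, and Protocol 11.4.2 describes the local reactogenicity comparison as formal. SAP 6.4 restricts serostatus subgroups to secondary and exploratory endpoints.

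**The concern.** Because dose follows enrolment group, anything that differs between the two groups of subjects is mixed with dose in the crude comparison: serostatus mix, calendar period, or reporting when the dose level is known. There is reason to take this seriously here. Enrolment was expected to take up to 15 months, in an area with active ZIKV and DENV transmission, and a hurricane disrupted Group 1. The SAP itself measures baseline serostatus in order to see whether it affects response to ZPIV.

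Two readings of the Table 43 p-values are at stake. A small p-value could be taken as a dose effect when part of it is group composition. A large one could be taken as similar reactogenicity when the data are too few to show that. An estimate with an interval, adjusted for the one measured baseline factor the trial was built around, would guard against both. A bare p-value guards against neither.

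**Working it through.** **Inputs from the documents.** Safety sample for the dose contrast: "approximately 45 active subjects in the 5.0 mcg dose group and 35 active subjects in the 2.5 mcg dose group" (Protocol 11.2). Test: Fisher's exact. No alpha is stated, so 0.05 two-sided is assumed. No event rates or serostatus shares are given, so those below are assumptions.

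**1. The plan's own figures.** The chance of seeing at least one event is 1 - (1 - rate)^n.
- n = 35, rate 4.5%: 1 - 0.955^35 = 80.04%.
- n = 80, rate 2.0%: 1 - 0.98^80 = 80.14%.

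Both match the stated 80%. They concern seeing an event at all and give no information on comparing doses.

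**2. What Fisher's test can show at 45 v 35.** By exact enumeration, its true size is 1.6% to 4.0% for common rates of 5% to 50%. Power is 43% for 40% v 20% and 77% for 50% v 20%. For rare events in the 5 mcg arm only:
- 5/45 v 0/35: p = 0.064
- 6/45 v 0/35: p = 0.033

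In the other direction, 4/35 v 0/45 also gives p = 0.033.

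**3. What an interval adds.** Difference = 5 mcg rate minus 2.5 mcg rate, with Newcombe 95% CI.

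| 5 mcg | 2.5 mcg | Fisher p | Difference (points) | 95% CI |
|---|---|---|---|---|
| 9/45 | 3/35 | 0.21 | 11.4 | -5.1 to 26.3 |
| 18/45 | 7/35 | 0.088 | 20.0 | -0.5 to 37.6 |
| 0/45 | 0/35 | 1.0 | 0 | -9.9 to 7.9 |

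None of these p-values is below 0.05. The intervals show that the first two results are compatible with differences above 25 points, and that even two zeros leave roughly 10 points open on one side and 8 on the other.

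**4. Possible bias from serostatus (assumed inputs).** With no true dose effect, crude difference = (difference in seropositive share) x (risk gap between serostatus groups).
- 0.20 x 0.20 = 4 points; 0.20 x 0.30 = 6 points.
- At the 6-point end (risks 50% v 20%, shares 60% v 40%), crude Fisher gives p < 0.05 in 6.4% of trials, against 3.6% with equal 50% shares.
- More extreme inputs do more. With risks 60% v 20%, the figure is 3.8% at equal 50% shares, 9.0% at 60% v 40% (8 points) and 26.5% at 70% v 30% (16 points).

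**5. What stratification does (invented counts).**
- Seropositive: 19/32 (5 mcg) v 7/11 (2.5 mcg). Seronegative: 3/13 v 5/24.
- Crude: 22/45 - 12/35 = 14.6 points (95% CI -7.0 to 34.1).
- Mantel-Haenszel numerator: (19x11 - 7x32)/43 + (3x24 - 5x13)/37 = -0.349 + 0.189 = -0.160.
- Denominator: (32x11)/43 + (13x24)/37 = 8.186 + 8.432 = 16.618.
- Stratified difference: -0.160/16.618 = -1.0 point.

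Fisher within each stratum gives p = 1.0 here. The planned subgroup rows would therefore hint at the answer, but they supply no combined estimate.

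**The case against.** **Serostatus is already handled.** Tables 43 and 12 repeat the tests within serostatus strata, and a within-stratum comparison cannot be confounded by the variable that defines the stratum. Table 17 shows serostatus by arm and Table 15 shows first-dose dates. This stands: a reader might infer that the SAP ignores serostatus, and it does not. Separate strata can also be read as meeting the stratification sentence in Protocol 11.1, so the absence of a pooled estimate is a gap rather than a plain breach. The cover is less secure than it looks, though, because SAP 6.4 read literally would exclude those subgroup rows from a primary endpoint.

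**A pooled estimate may be the wrong summary.** If serostatus modifies the dose effect, stratum results are the better answer. That is a reason to print both, and some strata may be too sparse to read alone.

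**Precision is not absent.** Tables 36 and 45 give each arm's rate with an exact interval, so a crude difference can be derived. Its interval and an adjusted version cannot be read off.

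**The study is exploratory.** Both documents say so, and the SAP nowhere claims that a small p-value proves a dose effect. That is fair, but a study with no hypothesis to test has more use for estimates and intervals than for p-values.

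**Drift between enrolment periods.** A reader might infer that splitting placebo by group would settle this. With about 5 v 5 it would not: 3/5 v 0/5 gives p = 0.17, and 4/5 v 0/5 is needed for p = 0.048. Nor do the documents support treating enrolment as strictly sequential, since some overlap is permitted. Overlap would still not make dose a randomised factor.

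**Conclusion.** The point holds as a gap in the planned analysis. The dose contrast is non-randomised and open by group, the SAP does not say so, and the All-Subjects rows of Table 43 give it unadjusted p-values with no between-dose difference, interval or pooled serostatus adjustment.

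The firmest part is precision. At 45 v 35, a true 40% v 20% difference would be missed more often than found (power 43%), so a non-significant result cannot be taken as similarity.

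The bias part is conditional. The 4-6 points rest on an assumed 20-30 point risk gap and an assumed 20-point imbalance, and are small beside an interval about 31 points wide (-5 to 26). A reader might infer that a serostatus or period difference will be reported as a dose effect. The documents show no imbalance, so that remains a risk of interpretation.

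**What to change.** 1. **Table 43, All-Subjects rows:** add the 5 mcg minus 2.5 mcg risk difference with 95% CI, Mantel-Haenszel stratified by baseline ZIKV serostatus, beside the planned stratum-specific results. Give subjects with inconclusive serostatus their own stratum.
2. **Table 12:** add the same two-dose contrast. Its present test spans three groups, whereas endpoint 6 and Protocol 11.4.2 call for a between-dose comparison.
3. **SAP 6.4 and the Table 43 and Table 12 footnotes:** state that the dose contrast is non-randomised, open by group and descriptive.
4. **Reconcile** SAP 6.4 (serostatus subgroups for secondary and exploratory endpoints only) with Table 43, which serves a primary endpoint.
5. **Reconcile** SAP 4.4.3 (Group 2 after Group 1 is complete) with Protocol section 4 and SAP 4.1 (overlap permitted), using the first-dose dates in Table 15.

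Showing placebo by enrolment group is optional and descriptive only.

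The cost is SAP wording, an estimate-and-interval column in two tables, and modest programming. Serostatus is already collected, so no new data are needed.
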